### 4.3 REMOVAL OF SUBJECTS

A subject may be withdrawn from the study for any of the following reasons:

1. the event of the subject's death
2. the subject experiences an AE and the Investigator or the patient determines that withdrawal from the study is appropriate
3. a major protocol deviation that interferes with the integrity of the study data for this subject
4. the subject is noncompliant (does not comply with dosing instructions provided by the Investigator or does not comply with the study visit schedule) and the Investigator determines that withdrawal of the subject is appropriate
5. the subject withdraws consent to participate in the study
6. the site is unable to contact the subject after all reasonable efforts have been exhausted (Lost to Follow-Up)
7. any condition that, in the judgment of the Investigator, would compromise the ability of the subject to comply with the study protocol or complete the study
8. any subject who has to have "rescue" medication will be discontinued

A subject may decide to withdraw from the study at any time, for any reason, without prejudice to subsequent care or treatment by the Investigator.

Subjects who discontinue the study prematurely should be assessed in accordance with the end-of-treatment visit in [Section 6.8](#) and the follow-up procedures in [Section 5.12.1](#).

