#### **4.6 DEFINITIONS OF CONVERTER AND COMPLETER**

A converter is defined as a subject who has 3 consecutive monthly MAC-negative sputum cultures at any time within the first 6 months of the study.

Relapse or recurrence is defined as having MAC-positive sputum cultures in liquid broth media (agar negative) for 3 or more consecutive months, or having 1 MAC-positive sputum culture on solid media (agar positive) after achieving culture conversion.

A non-converter is defined as a subject who does not have 3 consecutive monthly MAC-negative sputum cultures at any time within the first 6 months of the study.

A completer for this study will be defined as follows:

1. A converter who successfully completes 12 months on the same treatment regimen beginning from the first of 3 negative cultures that defined conversion and successfully completes the 12 months off-treatment EOS follow-up visit.
2. A non-converter who successfully completes all dosing and protocol requirements up to and including the Month 6 study visit.

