## 5.10 PROHIBITED MEDICATIONS

Subjects are prohibited from using any inhaled antibiotics and any aminoglycosides with activity against MAC from 28 days before Day 1, and should not initiate these drugs during the study period unless clinically indicated as determined by the Investigator. If a subject requires an inhalational antibiotic for medical management of an acute pulmonary exacerbation secondary to Gram-negative bacteria during the study, then LAI should be interrupted during the course of that inhaled antibiotic treatment and until the acute event has resolved. Inhaled antibiotics such as tobramycin that do not have activity against MAC are permitted. Administration of LAI should begin again after the inhaled antibiotic is stopped and the acute event has resolved. During the course of an inhaled antibiotic treatment, the subject will remain in the study and complete all remaining study visits if possible. Exceptions include treatment with IV amikacin (or nebulized IV amikacin solution) and other aminoglycosides with activity against MAC, such as streptomycin or kanamycin. Such aminoglycosides for the treatment of NTM lung infection will be considered a “rescue” medication. If the Investigator believes that any of the aforementioned prohibited medications are necessary they must discuss these with the medical monitor and the subject will discontinue study drug and/or the study. Any questions about prohibited medications should be discussed with the medical monitor for the study.

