The Investigator must contact the medical monitor immediately before discontinuing a subject from study drug and/or study participation if possible, or no later than 1 business day after the event. When a subject is prematurely discontinued from study drug, the subject will be given the option to continue in the study, off study drug, until their Month 8 visit (except for subjects enrolled at sites in Japan. All subjects at sites in Japan who discontinue study drug will also discontinue study participation). When a subject is prematurely discontinued from study drug and/or study participation, the Investigator will clearly document the reason in the medical record and complete the appropriate eCRF page describing the reason for discontinuation. If the subject completes all study procedures (including those who discontinued study drug but remain in the study), up to and including the Month 6 study visit, and sputum results indicate non-conversion or relapse/recurrence, they will be invited to participate in a separate open-label study of LAI (Study INS-312), provided all entry criteria have been met for that study. Any subject who discontinues the study prior to the Month 6 study visit will not be eligible to participate in the separate open-label study of LAI (INS-312).

In the event that a subject is withdrawn from the study treatment because of an AE, the subject should be followed and treated by the Investigator until the abnormal parameter or symptom is resolved or stabilized. It is up to the Investigator to determine and document that the AE is either resolved or that it has reached a stable state, after which no further follow-up is necessary.

If a subject fails to complete scheduled assessments in the study, the Investigator must determine the reasons and the circumstances as completely and accurately as possible. "Lost to follow-up" should be marked only in an exceptional case when all documented attempts to reach the subject by the Investigator or other staff members were unsuccessful.

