## **9.5 ANALYSIS POPULATIONS**

### **9.5.1 Intent-to-treat Population**

The intent-to-treat (ITT) population is the set of all randomized subjects.

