## **9.6 EFFICACY ANALYSIS**

### **9.6.1 Primary Endpoint Analysis**

The primary efficacy endpoint is the proportion of subjects achieving culture conversion by Month 6. The primary efficacy analysis will be performed for the ITT population using the Cochran-Mantel-Haenszel test stratified by smoking status and prior multi-drug regimen (on treatment or off treatment for at least 3 months) at the 2-sided significance level of 0.05. The

Protocol Amendment #3 version: 22 February 2016

*This protocol is solely for the purpose of communicating information about the investigational drug between Insmad Incorporated and study personnel. Information is not to be reproduced, abstracted or used for sharing of information for any other purpose, whatsoever, except with the written permission of Insmad Incorporated.*

null hypothesis assumes that the culture conversion by Month 6 is independent of treatment, and the alternative hypothesis assumes that the culture conversion by Month 6 is associated with treatment. Subjects with missing sputum culture results for which culture conversion cannot be evaluated (3 consecutive monthly negative sputum cultures) will be considered as non-converters.

A supportive analysis of the primary efficacy endpoint will be performed for the PP populations similarly using the Cochran-Mantel-Haenszel test stratified by smoking status and prior multi-drug regimen.

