Supportive ANCOVA analyses of the change from Baseline to Month 6 in 6MWT distance with treatment arm and the randomization strata as factors, and the Baseline 6MWT distance as a covariate will also be performed for both the ITT and the PP populations. In the ANCOVA analysis for the ITT population, the last-observation-carried-forward method will be used to handle the missing data.

The changes from Baseline to Month 8 (exploratory endpoint), EOT, and 3 months off-treatment (exploratory endpoint) in 6MWT distance will be analyzed for the ITT population using the similar mixed-effects model for repeated measures (MMRM) with an unstructured covariance matrix implemented with SAS MIXED procedure over all post-randomization visits.

Kaplan-Meier estimates for the distribution of time to culture conversion will be constructed for treatment arms. The treatment comparison will be made using the stratified log rank test for the ITT population. The estimated median time to culture conversion for each treatment arm will be presented. The time to culture conversion will also be analyzed using Cox regression model to estimate hazards ratio.

The proportion of subjects achieving culture conversion with sustainability at the EOT and the proportion of subjects achieving culture conversion with durability after 3 months off-treatment will be analyzed for both the ITT and PP populations similarly using the Cochran-Mantel-Haenszel test stratified by smoking status and prior multi-drug regimen. Subjects who relapse, have “rescue” medication and/or die before reaching EOT for sustainability and 3 months off-treatment for durability will be considered as failure to achieving culture conversion.

Protocol Amendment #3 version: 22 February 2016

*This protocol is solely for the purpose of communicating information about the investigational drug between Insmmed Incorporated and study personnel. Information is not to be reproduced, abstracted or used for sharing of information for any other purpose, whatsoever, except with the written permission of Insmmed Incorporated.*

The change from Baseline (Day 1) to Month 6 in SGRQ total score and the SGRQ – Part 2 subdomain (exploratory endpoint) will be analyzed for the ITT population similarly using the same MMRM method as the analysis of the change from Baseline to EOT in 6MWT distance.

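### Rescue medication is scored as failure for the sustainability and durability endpoints but not for the primary conversion endpoint, and the protocol is inconsistent on whether rescue ends study participation

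*Protocol*

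**What the plan says.** **Primary endpoint.** Section 4.6 defines conversion by culture results alone: "A converter is defined as a subject who has 3 consecutive monthly MAC-negative sputum cultures at any time within the first 6 months". The primary analysis uses the intent-to-treat set: "The intent-to-treat (ITT) population is the set of all randomized subjects". The only scoring rule added in Section 9.6.1 concerns missing data: "Subjects with missing sputum culture results for which culture conversion cannot be evaluated (3 consecutive monthly negative sputum cultures) will be considered as non-converters".

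**Secondary culture endpoints.** Section 9.6.2 adds a clinical rule: "Subjects who relapse, have “rescue” medication and/or die before reaching EOT for sustainability and 3 months off-treatment for durability will be considered as failure". The sentence goes on to say that what has failed is the achievement of culture conversion. It covers sustainability and durability. The paragraph on time to culture conversion has no rescue rule.

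**What happens after rescue.** The protocol gives several answers.
- The synopsis (withdrawal criteria) and Section 4.3 list rescue among the reasons for withdrawal from the study.
- Section 5.9 and item 4 of Section 5.12 say only that such subjects are discontinued. Items 3 and 5 of the same list specify discontinuation from the study; item 4 does not.
- Section 5.10 defines aminoglycosides active against MAC, including IV amikacin, as rescue when given for the NTM infection. It then says of prohibited medications that "the subject will discontinue study drug and/or the study".
- Section 5.12 says that on stopping study drug early "the subject will be given the option to continue in the study, off study drug, until their Month 8 visit", except at sites in Japan, where stopping study drug also ends participation.

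**The concern.** If a rescued subject remains in the study, monthly sputum cultures continue and are observed, so the missing-culture rule does not apply. Three consecutive negatives obtained on rescue would make that subject a converter in the primary analysis, while Section 9.6.2 would call the same subject a failure to convert.

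The trial is open-label, so the decision to rescue may differ between arms. Rescue can be parenteral amikacin, which has the same active ingredient as LAI. A conversion obtained on it would be credited to the randomised arm. With an expected control rate of only 5%, a few such subjects could move the primary comparison.

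**Working it through.** **Step 1: can the situation arise?** It needs three things.
1. *No rescue condition in the primary rule.* True of Sections 4.6 and 9.6.1.
2. *A rescued subject still supplying cultures.* Not possible if rescue means withdrawal from the study (Section 4.3). Possible if it means stopping study drug only (Section 5.10) followed by the stay-in option (Section 5.12), outside Japan.
3. *Three negatives by Month 6.* The first must come by Month 4, and rescue must start before the third.

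So the route exists on the text, but it is narrow. It fits LAI subjects best: Section 5.8.5 equates study drug with LAI, so a control subject has no study drug to stop.

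**Step 2: reproduce the plan's sample size (Section 9.1).** Inputs: 5% control, 20% LAI, allocation k = 2, two-sided 0.05, 90% power, continuity-corrected chi-square.

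Pooled rate = (0.05 + 2 × 0.20)/3 = 0.15.

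Uncorrected control n = [1.960 √(3 × 0.15 × 0.85) + 1.2816 √(2 × 0.05 × 0.95 + 0.20 × 0.80)]² / (2 × 0.15²) = 76.82.

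Corrected n = (76.82/4) × [1 + √(1 + 2 × 3/(76.82 × 2 × 0.15))]² = 86.5, rounded up to 87.

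Total = 87 + 174 = 261, which matches the plan.

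**Step 3: power formula.** Power = Φ{(d − c − 1.960 × SE0)/SE1}, where d is the difference in rates, c = ½(1/n1 + 1/n2), SE0 uses the pooled rate and SE1 the separate rates.

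At 87/174, 5% vs 20%: (0.15 − 0.00862 − 1.960 × 0.04689)/0.03828 = 1.293, so power is 90.2%.

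With 3 points added to control (8% vs 20%): (0.12 − 0.00862 − 1.960 × 0.04814)/0.04202 = 0.405, so power is 65.7%.

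**Step 4: illustration over assumed additions.** The protocol gives no rescue rate, so every addition below is an assumption. The primary set is all randomised subjects, up to about 351, which at 2:1 is 234/117. That size is shown too, assuming that 20% and 5% hold for everyone randomised.

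| Added conversions (percentage points) | Control only, 174/87 | Control only, 234/117 | Both arms equally, 174/87 |
|---|---|---|---|
| 0 | 90.2% | 97.4% | 90.2% |
| 1 | 83.6% | 94.2% | 88.0% |
| 2 | 75.2% | 88.9% | 85.8% |
| 3 | 65.7% | 81.3% | 83.8% |

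The control-only additions of 1, 2 and 3 points are 0.9, 1.7 and 2.6 subjects of 87, or 1.2, 2.3 and 3.5 of 117.

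**Step 5: the other direction.** Suppose there is no true effect (5% in each arm) and rescue-assisted conversions occur in the LAI arm only. The exact chance of p < 0.05 at 174/87 is 2.3% with 1 added point, 3.8% with 2 and 6.6% with 3. Three points is about 5 of 174 subjects.

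**The case against.** The other side has several fair points.

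- **Rescue mostly ends participation.** The synopsis and Section 4.3 say so, and the and/or wording in Section 5.10 covers prohibited medications more widely than rescue. Subjects who leave lack later cultures and become non-converters by default unless already converted. This stands, and it limits how many subjects are affected.
- **The control-only figures model the less likely arm.** This stands. The stay-in option is written for subjects who stop study drug, which fits LAI subjects better.
- **Early rescue should be uncommon.** Sites do not see study cultures until the Month 6 result is known (Section 3.1), and Section 7.1.1 strongly discourages local mycobacterial cultures, so non-conversion itself is not an obvious trigger. If 20% of rescued subjects converted (an assumption), 3 added points would need 0.03/0.20 = 15% of controls, about 13 of 87, to be rescued early and stay in. This stands.
- **Analysing observed cultures regardless of rescue is a legitimate treatment-policy choice, and endpoints with different time windows may carry different failure rules.** True in general. But the protocol does not state that choice for the primary, and its own rule for the later endpoints describes rescue as failing to achieve conversion, the same outcome that the primary measures.
- **The analysis plan may settle it.** It may add detail, but the protocol itself already fixes a rescue rule for two culture endpoints and a narrower rule for the primary.

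A reader might infer that the primary result is biased in favour of LAI, or that power really falls to about 66%. The documents support neither. They give no rescue frequency and no split by arm. Control rescue would work against LAI, and rescue in the LAI arm would work for it.

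**Conclusion.** The inconsistency is real and is in the protocol's own text: a subject can be a primary converter and, because of rescue, a failure to convert in the secondary culture endpoints. Whether this can happen depends on discontinuation wording that does not agree across sections.

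The likely effect is small and of unknown direction. The power and error figures show sensitivity to assumed additions; they do not predict what will happen. The planned sample size is reproduced and is not in dispute. If rescue before conversion is scored as non-conversion and the design rates of 20% and 5% are kept, N = 261 and power of 90.2% are unchanged. The point deserves correction because the change is cheap and the primary endpoint rests on few control events.

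**What to change.** 1. In Section 9.6.1, state that a subject who starts rescue anti-mycobacterial medication before the third of the three qualifying negative cultures is analysed as a non-converter, consistent with Section 9.6.2. Rescue after the third negative leaves primary status unchanged and is picked up by the existing rule for sustainability and durability.
2. Apply the same scoring to time to culture conversion, so that no conversion event is counted for such a subject.
3. Add a sensitivity analysis of the primary endpoint on observed cultures regardless of rescue.
4. Reconcile the synopsis withdrawal criteria with Sections 4.3, 5.9, 5.10 and 5.12 on whether rescue ends study drug or study participation, and say how this applies to control subjects. Which clinical rule is right is for the sponsor and is not proposed here.

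The cost is one sentence in Section 9.6.1, a matching line for time to conversion, one extra analysis and an editorial reconciliation. The downside is a possibly slightly lower conversion rate in either arm.

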### 9.6.2 Secondary Endpoint Analyses

The change from Baseline (Day 1) to Month 6 in 6MWT distance will be analyzed for the ITT population (assuming Missing-Not-at-Random [MNAR]) using a model under the pattern-mixture model framework. This model assumes that subjects on the LAI plus a multi-drug regimen arm with missing data follow the response distribution of a multi-drug regimen alone arm. It involves 3 steps:

1. The posterior mean and covariance estimates from the SAS MI procedure using the available non-missing data of a multi-drug regimen alone arm will be utilized to multiply impute missing data.
2. The endpoint will then be analysed for each complete data set with imputed data using an analysis of covariance (ANCOVA) with treatment arm and the randomization strata as factors, and the Baseline 6MWT distance as a covariate.
3. The treatment LSMEAN differences will be averaged and the associated standard errors will be summarized based on within-imputation and between-imputation variances using the SAS MIANALYZE procedure, to yield a final estimate of treatment contrast with associated 95% confidence interval (CI) and p-value.

A sensitivity analysis of the change from Baseline (Day 1) to Month 6 in 6MWT distance will be performed using a mixed-effects model for repeated measures (MMRM) with an unstructured covariance matrix implemented with SAS MIXED procedure over Months 4 and 6. This model

Protocol Amendment #3 version: 22 February 2016

*This protocol is solely for the purpose of communicating information about the investigational drug between Insmad Incorporated and study personnel. Information is not to be reproduced, abstracted or used for sharing of information for any other purpose, whatsoever, except with the written permission of Insmad Incorporated.*

will include treatment, month, the treatment-by-month interaction, smoking status and prior multi-drug regimen (on treatment or off treatment for at least 3 months) as fixed factors, the Baseline (Day 1) 6MWT distance as a covariate, as well as the Baseline 6MWT distance-by-month interaction. The Kenward-Rogers correction for denominator degrees of freedom, standard errors, and test statistics will be utilized. The between-treatment difference in Least Squares (LS) mean change from Baseline to Month 6, the corresponding 95% CI for the true between-treatment difference, and the p-value will be presented.

Supportive ANCOVA analyses of the change from Baseline to Month 6 in 6MWT distance with treatment arm and the randomization strata as factors, and the Baseline 6MWT distance as a covariate will also be performed for both the ITT and the PP populations. In the ANCOVA analysis for the ITT population, the last-observation-carried-forward method will be used to handle the missing data.

The changes from Baseline to Month 8 (exploratory endpoint), EOT, and 3 months off-treatment (exploratory endpoint) in 6MWT distance will be analyzed for the ITT population using the similar mixed-effects model for repeated measures (MMRM) with an unstructured covariance matrix implemented with SAS MIXED procedure over all post-randomization visits.

Kaplan-Meier estimates for the distribution of time to culture conversion will be constructed for treatment arms. The treatment comparison will be made using the stratified log rank test for the ITT population. The estimated median time to culture conversion for each treatment arm will be presented. The time to culture conversion will also be analyzed using Cox regression model to estimate hazards ratio.

The proportion of subjects achieving culture conversion with sustainability at the EOT and the proportion of subjects achieving culture conversion with durability after 3 months off-treatment will be analyzed for both the ITT and PP populations similarly using the Cochran-Mantel-Haenszel test stratified by smoking status and prior multi-drug regimen. Subjects who relapse, have “rescue” medication and/or die before reaching EOT for sustainability and 3 months off-treatment for durability will be considered as failure to achieving culture conversion.

Protocol Amendment #3 version: 22 February 2016

*This protocol is solely for the purpose of communicating information about the investigational drug between Insmmed Incorporated and study personnel. Information is not to be reproduced, abstracted or used for sharing of information for any other purpose, whatsoever, except with the written permission of Insmmed Incorporated.*

The change from Baseline (Day 1) to Month 6 in SGRQ total score and the SGRQ – Part 2 subdomain (exploratory endpoint) will be analyzed for the ITT population similarly using the same MMRM method as the analysis of the change from Baseline to EOT in 6MWT distance.

### **9.6.3 Exploratory Endpoint Analyses**

The change in 6MWT distance at Month 6 for converters compared with non-converters overall for ITT population, within LAI plus a multi-drug regimen, within the multi-drug regimen alone, the change in BMI at Month 6 for LAI plus a multi-drug regimen compared with a multi-drug regimen alone, and the changes in chest CT scan at EOT for LAI plus a multi-drug regimen compared with a multi-drug regimen alone in a sub-set of subjects will be analyzed using the ANCOVA models with the comparison arm (converters vs. non-converters or the treatment arm) and the randomization strata as factors, and the corresponding Baseline measure as a covariate. If a CT scan is not performed at EOT for any subject, then prior CT scan will be used in the analysis.

The change from Baseline (Day 1) to Month 6 and EOT in the EQ-5D-3L patient reported health outcomes will be analyzed for the ITT population similarly using the same MMRM method as the analysis of the change from Baseline to EOT in 6MWT distance. Kaplan-Meier estimates for the distribution of time to death will be constructed by treatment arm. The treatment comparison will be made using the stratified log rank test for the ITT population. Incidence of new MAC strains will be summarized by treatment arms.

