### 3.4 EXPLORATORY ENDPOINTS

1. Change in 6MWT distance at Month 6 for converters versus non-converters in LAI arm
2. Change in 6MWT distance at Month 6 for converters versus non-converters for all subjects
3. Change in 6MWT distance at Month 6 for converters versus non-converters in the multi-drug regimen alone arm
4. Change in BMI at Month 6 in LAI arm compared to a multi-drug regimen alone
5. Change in 6MWT distance at Month 8 and 3 months off-treatment in the LAI arm compared to multi-drug regimen alone

Protocol Amendment #3 version: 22 February 2016

*This protocol is solely for the purpose of communicating information about the investigational drug between Inmed Incorporated and study personnel. Information is not to be reproduced, abstracted or used for sharing of information for any other purpose, whatsoever, except with the written permission of Inmed Incorporated.*

Confidential

6. Proportion of subjects achieving culture conversion with durability after 12 months off treatment (EOS) in the LAI arm compared to a multi-drug regimen alone
7. Change from Baseline (Day 1) at Month 6 in the SGRQ – Part 2 (Activities of Daily Living)
8. Change from Baseline (Day 1) at EOT in the EQ-5D-3L
9. Proportion of subjects who develop a new strain of MAC in the LAI arm compared to multi-drug regimen alone
10. Radiological changes in CT scan, within a sub-set of subjects, at EOT in the LAI arm compared to multi-drug regimen alone, where appropriate
11. Mortality at EOS

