## **9 STATISTICS**

### **9.1 SAMPLE SIZE**

The sample size was determined for the primary comparison between the treatment arms LAI plus a multi-drug regimen and a multi-drug regimen alone with respect to the proportion of subjects achieving culture conversion by Month 6 using nQuery Advisor® 7.0. Assuming a culture conversion rate by Month 6 of no less than 20% for the LAI plus a multi-drug regimen treatment arm, the rate by Month 6 of 5% for the multi-drug regimen alone treatment arm, and a 2:1 randomization ratio, a sample size of 261 subjects (174 for LAI plus a multi-drug regimen and 87 for the multi-drug regimen) will provide at least 90% power for the continuity-corrected Chi-square test at the 2-sided significance level of 0.05.

Protocol Amendment #3 version: 22 February 2016

*This protocol is solely for the purpose of communicating information about the investigational drug between Insmmed Incorporated and study personnel. Information is not to be reproduced, abstracted or used for sharing of information for any other purpose, whatsoever, except with the written permission of Insmmed Incorporated.*

The sample size was also evaluated for the secondary endpoint of change from Baseline to Month 6 in 6MWT distance. Assuming a common standard deviation of 100 and a 2:1 randomization ratio to either LAI plus a multi-drug regimen or a multi-drug regimen alone, a sample size of 192 subjects (128 for LAI plus a multi-drug regimen and 64 for the multi-drug regimen) will provide at least 90% power to detect a between-treatment difference of 50 meters in mean change from Baseline to Month 6 in 6MWT distance using a two arm t-test at the 2-sided significance level of 0.05.

Due to lack of durability data, it is difficult to estimate the power with a total sample size of 261 subjects for the comparison between treatment arms with respect to the proportion of subjects achieving culture conversion with durability after 3 months off-treatment. Assuming the proportion of subjects achieving culture conversion with durability is 16% and 4% for LAI plus a multi-drug regimen and a multi-drug regimen respectively, and a 2:1 randomization ratio, a sample size of 261 subjects (174 for LAI plus a multi-drug regimen and 87 for the multi-drug regimen) will provide at least 83% power for Fisher's exact test at the 2-sided significance level of 0.05.

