## **9.2 STRATIFICATION**

Subjects will be stratified by smoking status (current smoker or not) and prior multi-drug regimen (on treatment or off treatment for at least 3 months) at Screening.

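### The all-subject converter versus non-converter 6MWT ANCOVA omits treatment arm, so at the planning rates it absorbs about a quarter of any direct LAI effect

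*Protocol*

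**What the plan says.** Section 3.4 lists three converter comparisons of the Month 6 change in walking distance: within the LAI arm ("Change in 6MWT distance at Month 6 for converters versus non-converters in LAI arm"), within the control arm, and pooled ("Change in 6MWT distance at Month 6 for converters versus non-converters for all subjects").

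Section 9.6.3 covers all three, plus two treatment comparisons (BMI and chest CT), with one template: "ANCOVA models with the comparison arm (converters vs. non-converters or the treatment arm) and the randomization strata as factors", and the matching Baseline measure as covariate. The wording allows one group factor per model. For the pooled converter comparison that factor is conversion status.

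Treatment arm does not enter through the strata either. Section 9.2 states: "Subjects will be stratified by smoking status (current smoker or not) and prior multi-drug regimen". No other section adds arm to this model. The supportive treatment ANCOVA of the same Month 6 outcome in Section 9.6.2 does carry it ("6MWT distance with treatment arm and the randomization strata as factors, and the Baseline 6MWT distance as a covariate"), although there arm is the comparison under test.

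**The concern.** The trial is designed on the expectation that LAI raises conversion, so converters should be disproportionately LAI subjects. In a pooled model without arm, any effect of LAI on walking distance at a fixed conversion status is partly credited to conversion.

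The protocol's own figures make such a direct effect plausible. Section 9.1 plans for a 50 m total difference and a conversion difference of 15 percentage points. For all 50 m to act through conversion, each conversion would have to be worth 50/0.15 = 333 m, more than three times the assumed SD of 100 m. The study is also open-label. Section 7.2.1.2 blinds the person conducting the walk test, but the subject knows the treatment, and the test depends on the subject's effort.

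At stake is how endpoint 2 is read. The pooled result could differ from both within-arm results purely because of the mix of arms, and an apparent benefit of conversion could in part be a relabelled treatment effect.

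**Working it through.** **Inputs.** From Section 9.1:
- conversion rates: "Assuming a culture conversion rate by Month 6 of no less than 20% for the LAI plus a multi-drug regimen treatment arm", and 5% for control
- 174 LAI and 87 control subjects
- for walking distance: "Assuming a common standard deviation of 100 and a 2:1 randomization ratio", and a planned difference of 50 m

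The direct effect *D* (LAI minus control at the same conversion status, taken as equal in converters and non-converters) is not given in the protocol. It is an assumption, shown at 25 m and 50 m.

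**Step 1: the plan's own sample size reproduces.** For 5% vs 20%, 2:1, 90% power and two-sided 0.05, the uncorrected control-arm size is 77. With the continuity correction it is 87, giving 87 + 174 = 261. Continuity-corrected power at that size is 90.2%, against the stated minimum of 90%. For walking distance, 64 + 128 subjects give 90.4% power, also as stated.

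**Step 2: arm mix by conversion status.**

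| | LAI | Control | Total | LAI share |
|---|---|---|---|---|
| Converters | 174 × 0.20 = 34.8 | 87 × 0.05 = 4.35 | 39.15 | 34.8/39.15 = 0.889 |
| Non-converters | 139.2 | 82.65 | 221.85 | 139.2/221.85 = 0.627 |

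Gap = 0.889 − 0.627 = 0.261 (unrounded).

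**Step 3: bias.** With arm omitted, the expected conversion coefficient is the within-arm conversion effect plus *D* × gap.
- *D* = 50 m: 50 × 0.261 = 13.1 m
- *D* = 25 m: 25 × 0.261 = 6.5 m
- a harmful direct effect gives the same size with the opposite sign

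**Step 4: bias against precision (SD 100).**
- SE without arm = 100 × √(1/39.15 + 1/221.85) = 17.3 m, so the bias is 13.1/17.3 = 0.75 SE and 6.5/17.3 = 0.38 SE.
- SE within LAI = 100 × √(1/34.8 + 1/139.2) = 19.0 m.
- SE within control = 100 × √(1/4.35 + 1/82.65) = 49.2 m.
- SE with arm in the pooled model = 1/√(1/19.0² + 1/49.2²) = 17.7 m, about 2% larger. The weight on LAI is (1/19.0²)/(1/19.0² + 1/49.2²) = 0.87.
- The squared correlation between arm and conversion is 0.198² = 0.039, and 1/√(1 − 0.039) = 1.02, which agrees with the 2%.

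**Step 5: error rate when conversion has no effect** (simulation, 261 subjects, nominal 5%, 20,000 trials per scenario, no strata or Baseline terms).

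| *D* | Arm omitted | Arm included |
|---|---|---|
| 50 m | 10.9% | 5.1% |
| 25 m | 6.7% | 5.0% |
| −25 m | 6.5% | 5.0% |

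A separate run of 2,000 trials with two strata at assumed prevalences, *D* = 50 m, gave a mean coefficient of 12.8 m and 11.6% rejection without arm, against 0.0 m and 5.1% with it.

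**Step 6: sensitivity to the conversion rates (LAI vs control).**

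| Rates | Gap |
|---|---|
| 20% vs 10% | 0.160 |
| 30% vs 10% | 0.248 |
| 16% vs 4% (durability rates, Section 9.1) | 0.253 |
| 25% vs 6.7% (Day 84 negative cultures in TR02-112) | 0.265 |
| 30% vs 5% | 0.327 |

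**The case against.** The strongest reply is that this is a bias only against a question the protocol does not ask. The objective is to compare all converters with all non-converters, and as a marginal description the arm-free contrast answers that. On this reading the 10.9% is not a false-positive rate, because the groups really do differ in that scenario. This is fair as far as it goes. But a pooled difference that partly reflects who was given LAI tells the reader little about conversion, and the treatment effect is already analysed elsewhere.

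Second, the within-arm comparisons are prespecified and free of the problem, and the corrected pooled estimate, with 87% of its weight on LAI, largely repeats the LAI one. That lowers the stakes. It does not repair endpoint 2, and the control-arm comparison would have only about 4 converters. Those few converters also mean that a common conversion effect across arms could hardly be checked.

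Third, the calculations use 261 subjects, while the ITT population may reach about 351. The gap depends on the rates and not on the total. At the same rates the SE would be 17.3 × √(261/351) = 14.9 m and the bias at 50 m 13.1/14.9 = 0.88 SE, so the conclusion is unchanged. Subjects who cannot be evaluated count as non-converters, which would shift the rates; Step 6 shows the effect of other rates. The weighted-average description of the pooled estimate is exact only without covariates and approximate for the model specified.

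Fourth, extra covariates can be left to a SAP. Here, however, the protocol names the factors.

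Finally, conversion is a post-randomization status, so other confounding remains whatever is done about arm. That stands and limits how the result should be read.

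**Conclusion.** The point holds. As written, the pooled converter model has no treatment term, and at the planning rates its conversion coefficient absorbs about 26% of any direct LAI effect on walking distance (16% to 33% over the other rates tried). That is 13.1 m for an assumed 50 m direct effect and 6.5 m for 25 m. If there is no direct effect there is no bias.

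The consequence is modest: the endpoint is exploratory, no alpha or power is attached to it, and the bias stays below one SE. It is nevertheless avoidable at almost no cost, so the change should be made, although nothing in the primary or secondary analyses depends on it.

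**What to change.** Add one sentence to Section 9.6.3: *For the overall converter versus non-converter comparison, treatment arm will also be included as a factor.* Leave the two within-arm models as they are. State that the result is to be interpreted as an association, because conversion is observed after randomization and adjusting for arm does not remove other confounding.

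The cost is one model term on data already held and an SE about 2% larger (17.3 m to 17.7 m). In exchange, the pooled estimate becomes approximately the precision-weighted average of the two within-arm contrasts. The change is best made before the Month 6 analysis.
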